1.0 Objectives / Specific Aims

To improve health care delivery to minority patients with SLE at highest risk for poor outcomes, utilizing patient navigators to address barriers to care related to access to preventive and specialty healthcare, medication adherence, and health literacy.

2.0 Background

Despite recent progress in the diagnosis and treatment of SLE, minorities continue to bear the greater burden of disease with disproportionately higher morbidity and mortality compared to white patients with SLE (1). Longitudinal studies of patients with SLE demonstrate a strong genetic component impacting the development of SLE and the risk of severe disease (2); however the development of irreversible SLE-related and medication-related organ damage is undeniably complicated by patient socioeconomic factors (2, 3). Patients frequently are sent home from clinic or the hospital with powerful immune suppressants and an incomplete understanding of risks and benefits. In the lupus Medicaid population, a large fraction of patients have medication non-adherence leading to increased risk of hospitalization (4). Every year 25% of SLE patients are hospitalized and 16% of those are readmitted within 30 days (5). Other factors associated with poor outcomes include transportation (6) and family caregiving obligations among others. Patients return with either complications of inappropriate treatment or organ failure (nephritis, pulmonary hemorrhage) from their disease.

Although we cannot change the patient's genetic risk factors or socioeconomic status, we can identify and modify the barriers to SLE care that lead to poor health outcomes (such as difficulty accessing primary and specialty healthcare, low health literacy, harmful attitudes and beliefs regarding SLE and its treatment).

3.0 Intervention to be studied

Patient navigator programs have been utilized successfully to improve health outcomes by reducing barriers to care for patients with several chronic diseases, including cancer, diabetes, HIV/AIDS, cardiovascular disease, and chronic kidney disease. A recent systematic review of patient navigator interventions found that 45 of the 67 randomized controlled trials reported statistically significant improvements in the primary outcomes (7). Since the first patient navigation program in the 1980s focused on breast cancer outcomes, there has been over a decade of successful use of patient

navigators in oncology. Consequently, for accreditation, cancer centers are required by the American College of Surgeons Commission on Cancer to provide patient navigation services as of 2015 (<https://www.facs.org/quality-programs/cancer>).

The navigator services most commonly provided include facilitation/coordination of care, practical support, including transportation and financial assistance, appointment scheduling and reminders, education and psychosocial support (7). The most effective patient navigators address both health system barriers and patient barriers (examples shown in Table 1).

Targeted interventions have been proposed to address the common barriers to care among patients with SLE (8-10), but a comprehensive patient navigator approach utilizing novel interventions based on evidence from prior studies, such as the one proposed, has yet to be described in the literature.

Table 1 - Features of the proposed Lupus Patient Navigator Program.

| Barriers to Optimal Care | Lupus Patient Navigator Program Features | Examples of Patient Navigator (PN) Interventions |
|---|--|---|
| Missed / Forgotten / Cancelled Appointments | Facilitate care (referrals, communication, coordination) / Appointment scheduling / Appointment reminder calls | Patient unable to navigate scheduling system to make specialist appointments; PN facilitates by contacting specialty offices and coordinating appointments based on patient's location needs. |
| Lack of Reliable Transportation | Practical support with transportation options | Pt is unfamiliar with transportation option in their area; PN provided public transportation schedules, instruction on how to schedule Medicaid van. |
| Lack of Information / Misinformation | Health literacy promotion, delivery of culturally tailored health information addressing patient and caregiver attitudes and beliefs | PN discovers patient and caregiver misperceptions about Lupus; PN provides publicly available resources from the Lupus Foundation of America website. |

| | | |
|-----------------------------|--|---|
| Poor Adherence to Treatment | Encouragement of treatment adherence through the use of medication diary / Assistance with enrolling into medication assistance programs | Patient unable to obtain medications due to lack of insurance; Assist patient with completing pharmaceutical patient assistance applications. |
| Financial Concerns | Practical support in finding community financial resources and public insurance options | Patient reports difficulty with utility bills; PN helps contact appropriate agencies for assistance. |

4.0 Study Endpoints

Improvement in Medication Adherence, Improvement in patient-reported lupus-specific disease status (measured by the LupusPRO), Improvement in Adherence with Primary Care / Specialty Care Visits, Lab and other Study Appointments.

Racial Discrimination will be measured using the validated 9-item Experiences of Discrimination (EOD) measure, which includes an index of racial discrimination experiences ever experienced. The EOD is a widely used and validated measure of racial discrimination. This short, self-report instrument is based on a prior instrument used in the Coronary Artery Risk Development in Young Adults (CARDIA) study validated in AA and Latino participants and has been previously used for measuring experiences of racial discrimination in AA women with SLE. (11).

5.0 Inclusion and Exclusion Criteria / Study Population

Criteria for Inclusion:

INTERVENTIONAL GROUP (n=25): 1) Self-identified Minority. 2) Patients ≥ 18 years of age as documented in the electronic medical record. 3) Meeting either American College of Rheumatology or SLICC Classification Criteria for SLE as documented in the electronic medical record (12, 13). 4) Ability to speak and understand English by self-report. 5) In the past six months having ≥ 1 missed clinic or diagnostic study/laboratory visit as documented in the electronic medical record, self-reported failure to adhere with prescribed medical therapy for SLE, or the participant is newly diagnosed with SLE. 6) In the past six months having been prescribed at least one immunosuppressive medication for SLE activity as documented in the electronic medical record regardless of whether taking the medication. 7) Have telephone access.

USUAL CARE GROUP (n=25): Meet criteria 1, 2, 3, 5, 6, 7 above for interventional group. All data from healthcare utilization and medication compliance will be collected via the CCCR biorepository request process. See data collection guidelines for this group below (Sections 12 & 13).

Criteria for Exclusion (Interventional Group only): 1) Unwilling or unable to give informed consent. 2) Being a prisoner or institutionalized individual. 3) Without telephone access. 4) Do not meet all of the inclusion criteria listed above.

Criteria for Exclusion (Usual Care Group only) 1) Do not meet usual care inclusion criteria above.

Recruitment will be enhanced by MUSC having specialized lupus clinics already in place dedicated to the care of patients with SLE.

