12.0 Data Management

The MUSC CCCR Patient Resource Core (Pro00021985) will act as an honest broker for the provision of clinical data of patients that fit criteria and are already enrolled in the CCCR study. The clinical data provided to the PN and PI of this study will include all data listed in sections 4.0 & 10.0 and will be provided to study staff de-identified. The data provided will only include 25 patient data sets for the "Usual Care" group that has not had contact with the patient navigator and serves as the control group for this study.

Analyses will be primarily descriptive in nature. Means, standard deviations, medians, inter-quartile ranges, and proportions will be reported on each outcome of interest, as appropriate. These statistics will be reported at baseline, 3 months, 6 months, and at 12 months for the primary outcome measure (Medication Adherence) and all secondary outcome measures. The secondary outcome measures are 1) Adherence with Primary Care and Specialty Care Visits, 2) Adherence with Lab and other Study Appointments, 3) Healthcare Utilization, 4) Disease-related Damage, 5) Corticosteroid Use and 6) Patient-Reported Outcomes.

In addition to results reported by our site, we will report results from our collaborating site, University of Alabama at Birmingham (UAB), during their implementation of the LPNP protocol.

Analyses will include estimates of site to site variability utilizing a combined MUSC and UAB dataset. All data sharing will be de-identified and maintained on MUSC's supported REDCap platform. Shared data and analyses were included in the Scope of Work executed by NIH subaward funding of 3P30AR072582-03S1, Improving Minority Health in Rheumatic Diseases.

Although this is not a randomized trial, we will use statistical methods such as propensity score weighting (36) to gain an understanding of how the use of PNs improves outcomes (e.g. medication adherence) when compared to usual care. Generalized linear mixed models will be used in conjunction with propensity score weighting to compare treatment group outcomes and estimate relevant effect sizes while adjusting for relevant baseline covariates (e.g. age, SLEDAI) and accounting for repeated measures within patients over time.

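### Entry criterion 5 overlaps with two of the improvement endpoints and no baseline window is defined, so uncontrolled within-group change is open to regression to the mean; the usual-care contrast is largely protected only if both groups are indexed and measured alike

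*Combined protocol and SAP*

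**What the plan says.** **Entry (Section 5.0).** Criterion 5 has three alternative routes. One is "In the past six months having ≥ 1 missed clinic or diagnostic study/laboratory visit as documented in the electronic medical record". The other two are "self-reported failure to adhere with prescribed medical therapy for SLE, or the participant is newly diagnosed with SLE". Usual-care patients must "Meet criteria 1, 2, 3, 5, 6, 7 above for interventional group", so criterion 5 applies to both groups and only criterion 4, on English, is dropped.

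**Endpoints (Section 4.0).** These are worded as improvement in medication adherence, in LupusPRO, and "Improvement in Adherence with Primary Care / Specialty Care Visits, Lab and other Study Appointments". No comparator appears in the definitions.

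**Analysis (Section 12.0).** "Analyses will be primarily descriptive in nature", with summaries at baseline and at 3, 6 and 12 months for the primary outcome (medication adherence) and all secondary outcomes. The section adds a comparison with usual care: "Generalized linear mixed models will be used in conjunction with propensity score weighting to compare treatment group outcomes and estimate relevant effect sizes". Age and SLEDAI are the covariates given as examples. Results from UAB will also be reported.

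**Timing and sources.** Section 6.0 identifies the usual-care patients after the navigator group has finished its visits and sets no index date for them. Section 10.0 gives navigator patients a medication diary from the baseline visit and takes usual-care adherence from pharmacy records. It does not say whether pharmacy records will also be used for the navigator group.

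**The concern.** Two of the three entry routes select on the behaviour whose improvement is later reported. A patient admitted because of a missed visit has, by construction, at least one miss in the preceding six months. Part of that is chance, and the chance part will not recur to the same extent. If those six months are the baseline, attendance will tend to rise afterwards whatever the navigator does.

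Attendance is a rate over a period, so a baseline value needs some pre-entry window. The eligibility look-back is the only such window the plan names. The diary starts at the baseline visit, so it cannot supply a pre-entry adherence value either.

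At stake is how the descriptive results are read. Section 12.0 says the pilot will inform the size of a definitive trial. A before-after change taken at face value would overstate what the navigator achieves.

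**Working it through.** The plan gives no figure on this point to reproduce, and no miss rates or visit counts. The inputs below are assumptions, shown as a range. Only the selection rule (at least one miss in six months) and the group size of 25 come from the plan.

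**Model.** Let n be scheduled visits per six months, m the mean miss probability and ρ the between-patient correlation, with beta-binomial miss counts and no navigator effect. Put s = 1/ρ − 1, a = m·s, b = (1 − m)·s.

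- Probability of no miss: P0 = B(a, b + n)/B(a, b); for ρ = 0, P0 = (1 − m)^n.
- Miss rate in the qualifying window, given at least one miss: m/(1 − P0).
- Expected rate in the next window for the same patients: [m − P0·a/(a + b + n)]/(1 − P0); for ρ = 0 this is m.
- Spurious fall: the difference between the last two.

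**Worked case, m = 0.15, n = 4.**

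- ρ = 0: P0 = 0.85^4 = 0.522. Window rate 0.15/0.478 = 0.314, next window 0.150, fall 16.4 points.
- ρ = 0.1: a = 1.35, b = 7.65, P0 = 0.5725. Window rate 0.15/0.4275 = 0.351. Next window (0.15 − 0.5725 × 1.35/13)/0.4275 = 0.212. Fall 13.9 points.
- ρ = 0.3: P0 = 0.653. Window rate 0.433, next window 0.329, fall 10.4 points.

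**Spurious fall in percentage points (ρ = 0 / 0.1 / 0.3).**

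| Visits per six months | m = 15% | m = 25% |
|---|---|---|
| 3 | 23.9 / 20.4 / 15.3 | 18.2 / 16.1 / 12.6 |
| 4 | 16.4 / 13.9 / 10.4 | 11.6 / 10.4 / 8.4 |
| 6 | 9.1 / 7.8 / 6.0 | 5.4 / 5.3 / 4.6 |
| 8 | 5.6 / 5.0 / 4.0 | 2.8 / 3.1 / 3.0 |
| 10 | 3.7 / 3.5 / 2.9 | 1.5 / 2.0 / 2.1 |

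The fall is 4.6 to 23.9 points with 3–6 visits and 1.5 to 5.6 points with 8–10. If baseline is instead measured in a fresh window after selection, the expected fall is zero.

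**What happens between groups.** This used 2,000 simulated null trials of 25 against 25, with m = 0.20, n = 4, ρ = 0.3, eight follow-up visits and the qualifying window as baseline. The exact calculation for these inputs takes the miss rate from 45.5% to 36.1%, a fall of 9.4 points.

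| Share entering by a missed visit, navigator / usual care | Navigator within-group t-test significant | Bias in difference in change | Between-group type I error |
|---|---|---|---|
| 100% / 100% | 47% | about 0 | 5.5% |
| 70% / 70% | 28% | about 0 | 5.7% |
| 100% / 50% | 45% | 4.5 points, favours navigator | 10.6% |
| 50% / 100% | 18% | 4.6 points, favours usual care | 10.8% |

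The remaining patients in each mix were drawn without selection on attendance. The simulation did not include propensity weighting. The plan specifies no within-group test; that column only shows how readily the artefact would look like an effect. Equal selection removes the bias, and unequal route mix brings some of it back, in either direction.

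**The case against.** The strongest reply is that the plan already has the right safeguard. Criterion 5 binds usual care too, and Section 12.0 asks how navigators improve outcomes relative to usual care, using weighted mixed models. Read with that section, improvement can mean a between-group difference. This stands: with equal selection the bias is about zero. It is incomplete, because the plan sets no usual-care index date, names different adherence sources for the two groups, and does not list entry route or prior attendance among the example covariates. Those covariates are only examples, so adjustment is not ruled out either.

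A second reply is that the visit count is assumed. Criterion 5 counts clinic, diagnostic and laboratory visits, so scheduled visits could be numerous and the artefact small. That also stands, and is why the 8–10 visit range is given.

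Several stronger readings are tempting, and the documents do not support them:

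- *Improvement is bound to appear even with an inert navigator.* The baseline window is undefined, and the newly diagnosed route does not select on adherence.
- *The primary outcome is biased by the amounts above.* The calculation concerns missed visits, a secondary outcome. Nothing in the documents allows a figure for medication adherence.
- *LupusPRO is affected in the same way.* Criterion 5 does not select on it.
- *Within-group change will be the planning effect.* No section says so. Section 12.0 ties effect sizes and preliminary effectiveness to differences between groups.
- *UAB results are uncontrolled.* Section 12.0 draws the 25 controls from the MUSC biorepository and does not say whether UAB has its own.

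**Conclusion.** The point holds as a cheap improvement to an under-specified plan; it does not show that the planned comparison is wrong as written. Within-group change in attendance is open to regression to the mean if the eligibility window is the baseline, as is likely for attendance. Under the stated assumptions the spurious fall, for patients entering by a missed visit, is about 5–24 points with 3–6 visits per six months and about 2–6 points with 8–10. Newly diagnosed entrants would dilute it. For medication adherence the same mechanism is plausible through the self-report route, but its size is unknown.

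The between-group contrast is largely protected on condition that both groups share the index-date rule, the entry-route mix and the adherence measure. The plan guarantees none of the three.

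**What to change.** **Section 4.0.** State the endpoints as the navigator versus usual-care difference in medication adherence and in visit and laboratory attendance over months 0–12.

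**Section 12.0.**

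- Exclude the six-month qualifying window, including the qualifying miss, from any change score.
- Apply one index-date rule to both groups.
- Use one adherence source, pharmacy records, for the comparison in both groups.
- Put criterion 5 entry route and, where available, attendance in months 7–12 before entry into the propensity or outcome model.
- State that within-group change, including any uncontrolled UAB change, is descriptive only and will not be used as the planning effect for the next trial.

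**Cost.** Wording in two sections, and an added item in the data request to the biorepository. That item is not a free chart look-up, because usual-care data arrive de-identified through an honest broker. Pharmacy records would also have to be obtained for the navigator group if they are not already planned. Headline improvement figures may be smaller. Some newly diagnosed patients will have no history for months 7–12, so the model needs a stated way to handle them.

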6.0 Number of Subjects

Sample size of n=25 patients in the Patient Navigation Group and n=25 patients in the Usual Care Group.

Patients who meet eligibility criteria and provide informed consent to participate in the LPNP will be enrolled up to the sample size goal of 25 patients. Upon completion of all study visits for the Patient Navigation Group, 25 additional patients who meet the inclusion criteria will be identified through the CCCR biorepository study to be included in the Usual Care group. Healthcare utilization and medication compliance data will be provided via a formal request (see Sections 12 & 13 below) to the CCCR and provided to study staff.

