10.0 Study Design / Methods

| Schedule of Events | Screening Call | In-Person Baseline Visit ^a | Monthly Call (Months 1,2,4,5,7,8,10,11) After Baseline* | Appointment Reminders (15 Days & 2 Days Before 3, 6, 9 Month Visit)** | Post 3, 6, 9 Month Visit ^a | Appointment Reminders (15 Days & 2 Days Before Post 12 Month Visit) | Post 12 Month Visit ^a |
|--|--|---------------------------------------|---|---|---------------------------------------|---|----------------------------------|
| Participation Assessment | X | | | | | | |
| Informed Consent & HIPAA | | X | | | | | |
| Steps To Care Intake Assessment Form | | X | | | | | |
| Steps To Care Reassessment Form | | | X | | X | | X |
| Participant Completed Assessments: Healthcare Resource Use Survey, Test of Functional Health Literacy | | X | | | | | |
| MacArthur Ladder, Experiences of Discrimination (EOD) measure | | X | | | | | X |
| LupusPRO | | X | | | X | | X |
| Medication Adherence Diary Review | | X | | | X | | X |
| Participant Completed Assessments: Perceived Stress Survey, Social Support Survey & Modified Picker Survey, Patient-Centered Care Questionnaire | | X | | | | | X |
| Appointment Reminder Calls | | | | X | | X | |
| Patient Satisfaction with Interpersonal Relationship with Navigator (PSN-I) survey | | | | | | | X |
| As Needed | | | | | | | |
| 1 Week F/U Call After Medication Change | Medication changes can occur at any time during the study. Medications to be included are those prescribed for your SLE. | | | | | | |

*Monthly Call window = +/- 7 calendar days.

**Appointment Reminder window = +/- 2 business days.

α All in person visits can be done in clinic or remotely via doxy.me

Screening:

PN will assess patient willingness to participate in the study as well as eligibility via a phone call, remote visit, in person at their clinic appointment, or once stable during an inpatient hospital stay.

Baseline In Person or Remote Visit:

Upon enrollment (Baseline visit) and signing of informed consent and HIPAA authorization, the PN will provide the following questionnaires, surveys and diaries:

- 1) Steps to Care Intake Assessment Form,
- 2) Healthcare Resource Use Survey,
- 3) LupusPRO survey,
- 4) Test of Functional Health Literacy,
- 5) Medication Adherence Diary,
- 6) Perceived Stress Survey,
- 7) Social Support Survey & Modified Picker Survey Patient-Centered Care Questionnaire,
- 8) Experiences of Discrimination (EOD) measure,

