For the Usual Care Group only: As stated above, in order to properly obtain data, while minimizing risk to patients in this study, the study staff will only utilize data for those patients that have already enrolled in the Division of Rheumatology Core Center for Clinical Research (CCCR; Pro21985). These patients will have provided properly executed HIPAA authorization to utilize Protected Health Information through the CCCR for optional research portions of the CCCR study (see General Comments of IRB application to review CCCR HIPAA Authorization). Data on healthcare utilization and adherence to prescribed medications based on pharmacy records would be collected on the Usual Care group as part of standard quality of care monitoring, which are allowed to be collected through the CCCR; Pro21985. This data will be provided through a formal request process, reviewed by the executive committee of the CCCR, and provided to this study's staff via this request. Note that this group of patients (Usual Care) will not have a formal informed consent process completed and executed as only analysis of data already collected for standard of care is necessary and falls under the HIPAA Authorization for the CCCR.

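### The self-report route in criterion 5 can be established by interview only in the navigator group, and the plan does not say how it is applied to record-only controls, so the groups may differ at entry on the primary outcome

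*Combined protocol and SAP*

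**What the plan says.** Criterion 5 in Section 5 (Inclusion and Exclusion Criteria) covers the past six months and can be met by any one of three routes. The first is "having ≥ 1 missed clinic or diagnostic study/laboratory visit as documented in the electronic medical record". The other two are "self-reported failure to adhere with prescribed medical therapy for SLE, or the participant is newly diagnosed with SLE", and neither is tied to the record. The usual-care group must "Meet criteria 1, 2, 3, 5, 6, 7 above for interventional group", so criterion 5 applies to it in full and only criterion 4 (English) is dropped.

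The two groups are assembled differently. For navigator patients, Section 10 says that "PN will assess patient willingness to participate in the study as well as eligibility via a phone call", or by a remote, in-person or inpatient contact. For the control group, Section 6 says that, once all navigator visits are complete, "25 additional patients who meet the inclusion criteria will be identified through the CCCR biorepository study". Section 10 adds that for these patients "only analysis of data already collected for standard of care is necessary" and that "adherence to prescribed medications based on pharmacy records would be collected on the Usual Care group". Section 12 describes a control group that "has not had contact with the patient navigator and serves as the control group for this study".

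Section 12 names medication adherence as the primary outcome. It plans propensity score weighting with generalized linear mixed models, and gives age and SLEDAI as examples of baseline covariates. Neither baseline adherence nor route of entry is named.

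**The concern.** Self-reported non-adherence is the only route into the study that is defined by the primary outcome, and the two groups can reach it by different means. A navigator candidate can be asked. A control qualifies this way only if someone had already written it down, and the plan does not say how such an entry would be found or abstracted.

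If more navigator patients than controls enter by this route, and those patients take less of their medication, the navigator group starts lower. A comparison of adherence levels during follow-up would then tend to understate the navigator's effect. A comparison of change from baseline would tend to overstate it, because patients selected for a recent lapse drift back towards their usual level. Section 4 words the endpoint as improvement, and Section 12 calls for treatment-group comparisons and effect sizes, so either bias could enter the estimates meant to support the design of a later randomized trial.

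**Working it through.** **Step 1. Set the sections side by side.**

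| Question | Navigator group | Usual-care group |
|---|---|---|
| Does criterion 5 apply? | Yes (Section 5) | Yes (Section 5) |
| How is eligibility assessed? | Live contact (Section 10) | CCCR search after navigator follow-up ends (Section 6) |
| Can self-report be sought? | Yes, by asking | Only if already recorded; no procedure stated |
| Adherence source described | Diary (Section 10) | Pharmacy records (Section 10) |
| Index date for the six months | Enrolment is the natural date | None defined |

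The criterion is the same; its ascertainment is not. Because the adherence sources differ too, no common baseline adherence measure is specified that could enter the propensity model.

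**Step 2. The plan's own figure.** Section 12 claims power above 80% for moderate differences in adherence, with 25 per group and two-sided alpha 0.05. For a single comparison in SD units, SE = √(2/25) = 0.283. Power of 80% needs (1.96 + 0.84) × 0.283 = 0.79 SD, and a 0.5 SD difference has 42% power. With three or four repeated measures, baseline adjustment and an assumed correlation of 0.3 to 0.7, a 0.5 SD difference has 76% to 91% power. As the plan does not quantify moderate, the claim can be neither confirmed nor refuted. I use 0.79 SD below as a reference effect.

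**Step 3. Size of a possible starting gap.** The documents give no inputs, so these are assumptions.

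- Shift b (SD) = (navigator share entering by self-report − control share) × (adherence deficit of those entrants, in SD).
- Rejection with no true effect = 1 − Φ(1.96 − b/0.283) + Φ(−1.96 − b/0.283).
- Power for a true 0.79 SD effect = Φ((0.79 − b)/0.283 − 1.96).

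| Share difference | Deficit | Shift b | Rejection, no effect | Power at 0.79 SD |
|---|---|---|---|---|
| 10 points | 0.5 SD | 0.05 | 5.4% | 75% |
| 10 points | 1.0 SD | 0.10 | 6.4% | 69% |
| 20 points | 0.5 SD | 0.10 | 6.4% | 69% |
| 20 points | 1.0 SD | 0.20 | 10.9% | 55% |
| 40 points | 0.5 SD | 0.20 | 10.9% | 55% |
| 40 points | 1.0 SD | 0.40 | 29.3% | 28% |
| 60 points | 0.5 SD | 0.30 | 18.6% | 41% |
| 60 points | 1.0 SD | 0.60 | 56.4% | 10% |

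The table applies to an unadjusted comparison of levels in which the whole starting gap persists. If only a fraction k persists, the level comparison is biased by k × b against the navigator and the change comparison by (1 − k) × b towards it.

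**Step 4. Cost of restricting the analysis.** If 20% to 60% of navigator patients qualified only by self-report (assumed), 5 to 15 of 25 would leave a restricted comparison.

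- 20 versus 25: SE = √(1/20 + 1/25) = 0.300, and power for 0.79 SD is about 75%.
- 10 versus 25: SE = √(1/10 + 1/25) = 0.374, and power is about 56%.

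**The case against.** A reader might go further and infer that controls lack the self-report route altogether. Section 5 says otherwise, and nothing in the documents says that the CCCR or the medical record holds no self-reported adherence. Section 12 even says the control dataset will contain everything listed in Sections 4 and 10. That sits badly with Section 10, which describes only utilization and pharmacy-record adherence for these patients, but it rules out asserting absence. It is also an inference that candidates are asked about missed medication: Section 10 says only that eligibility is assessed, and Section 8 adds referral by the rheumatologist, chart review and confirmation by the investigator.

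A reader might also infer that one stratum has no controls and that weighting therefore cannot help. The confounder is the level of adherence, not the label of the route. Controls who entered through missed visits may be poorly adherent too. The covariates in Section 12 are examples, not a closed list, so weighting on baseline adherence could reduce the gap if it were measured alike in both groups.

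Finally, this is a non-randomized pilot, mainly descriptive and sized chiefly for feasibility. That lowers the stakes but does not remove the point, because the plan also claims power and intends to estimate effects.

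What stands is that the plan gives no rule for applying the self-report clause to controls, and no named covariate or common baseline measure addresses the difference that may result.

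**Conclusion.** The point holds as a matter of unequal and unspecified ascertainment, not of different criteria. Followed as written, the plan can select the groups differently on baseline adherence. The imbalance is plausible rather than established, and its direction rests on the assumption that self-report entrants are the less adherent patients.

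Its size cannot be derived from the documents. With an assumed share difference of 20 to 40 points and a deficit of 0.5 to 1.0 SD, the shift is 0.10 to 0.40 SD. An unadjusted 5% test then rejects 6% to 29% of the time with no true effect, mostly against the navigator, and power for a true 0.79 SD effect falls from 80% to between 69% and 28%. With a share difference of 10 points, rejection is at most 6.4%. The matter should be settled before controls are selected.

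**What to change.** Make these changes before the control request goes to the CCCR:

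1. In Section 5, define record-verifiable entry for the comparison as a missed visit documented in the medical record, a new diagnosis, or a pharmacy-refill gap, each in the six months before a defined index date. State the index date for controls.
2. Run the same query on both groups and select controls on these routes.
3. Tabulate route of entry by group.
4. In Section 12, name baseline adherence from pharmacy records, measured the same way in both groups, as a covariate in the propensity model.
5. Keep all navigator patients in the main comparison and the descriptive results. Add a sensitivity analysis of the between-group adherence comparison limited to patients who meet a record-verifiable route.

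Navigator enrolment does not change, and because controls are chosen last the rule can still be fixed in advance. The costs are wording in Sections 5 and 12, and a refill look-back for navigator patients, for whom Section 10 now describes only a diary. The restricted analysis also loses precision: possibly 5 to 15 of 25 navigator patients under the assumed shares, fewer if the refill-gap route recaptures some. For that reason it belongs as a sensitivity analysis rather than as the main comparison.
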